IMPACT

Incidental Meningioma: Prognostic Analysis Using Patient Comorbidity and MRI-Tests

External validation and calibration of an incidental meningioma prognostic model – IMPACT: protocol for an international multicentre retrospective cohort study

Study sponsor	University of Liverpool [name] United Kingdom
Trainee leads	[name] [name]
Chief investigator	[name]
Version number and date	Version 6.0, 31 October 2020

Steering committee

[name] Academic Foundation Doctor University of Liverpool & Royal Liverpool University Hospital, Liverpool, UK

[name] Specialist Trainee in Neurosurgery & PhD candidate University of Liverpool & The Walton Centre NHS Foundation Trust, Liverpool, UK

[name] NIHR academic clinical fellow & specialist Trainee in Neurosurgery University of Oxford, Oxford, UK

[name] NIHR academic clinical fellow & specialist Trainee in Neurosurgery University of Manchester, Manchester, UK

[name] Consultant Clinical Oncologist The Clatterbridge Cancer Centre NHS Foundation Trust, Wirral, UK

[name] Professor of Medical Statistics University of Liverpool, Liverpool, UK

[name] Consultant Neuroradiologist The Walton Centre NHS Foundation Trust, Liverpool, UK

[name] Consultant Neurosurgeon The Walton Centre NHS Foundation Trust, Liverpool, UK

[name] Associate Professor & Hon. Consultant Neurosurgeon University of Leeds, Leeds, UK

[name] Consultant Neurosurgeon Cambridge University Hospitals NHS Foundation Trust, Cambridge, UK

[name] Professor of Neurosurgery & Hon. Consultant Neurosurgeon University of Liverpool & The Walton Centre NHS Foundation Trust, Liverpool, UK

STUDY SYNOPSIS

Short title External Validation of IMPACT

Study ID IMPACT

Study description An international multi-centre retrospective study of incidental meningioma to externally validate and calibrate a prognostic model of radiological and clinical progression – IMPACT (*Incidental Meningioma: Prognostic Analysis Using Patient Comorbidity and MRI Tests*).

Primary objective To externally validate the prognostic model IMPACT, i.e. to determine if IMPACT can accurately predict the clinical and radiological outcome of an incidental asymptomatic intracranial meningioma.

Secondary objectives

- To recalibrate the prognostic model IMPACT
- To determine the growth patterns of incidental meningiomas
- To examine the MRI and pathology features of meningiomas subject to surgical resection
- To determine the risk of post-intervention complications and tumour recurrence/growth for meningiomas subject to surgery, stereotactic radiosurgery, or fractionated radiotherapy
- To assess the economic implications of stratifying follow-up according to risk of disease progression

Study design Retrospective study of longitudinal radiological and clinical outcomes of incidental intracranial meningioma patients at participating centres diagnosed between 01/01/2009 and 31/12/2010. Data will be recorded until death or last date of follow-up.

Sample size 1500 patients

STUDY FLOWCHART

[figure not shown]

TABLE OF CONTENTS

STUDY SYNOPSIS	3
STUDY FLOWCHART	4
1 INTRODUCTION	6
1.1. THE IMPACT MODEL	7
2 OBJECTIVES	7
2.1. Primary objective	7
2.2. Secondary objectives	7
3 METHODS	7
3.1. Study design	7
3.2. Study population and eligibility criteria	7
3.3. Patient identification	8
3.4. Sample size	9
3.5. Study endpoints	9
3.6. Data collection	9
3.7. REDCap database	9
3.8. Recorded variables	10
3.9. Data quality assurance	13
3.10. Planned statistical analysis	14
4 ETHICS AND DISSEMINATION	16
4.1. Study registration	16
4.2. Local investigator responsibilities	16
4.3. Confidentiality and data protection	16
4.4. Ownership	17
4.5. Dissemination of results	17
4.6. Authorship eligibility	17
5 FUNDING	17
6 STUDY TIMELINE	18
7 CONCLUSION	18
8 REFERENCES	18
9 APPENDICES	20

1 INTRODUCTION

Meningiomas have the highest incidence rate amongst all primary central nervous system tumours. Descriptive studies from Europe and North America suggest this rate to be between 4.20 and 8.58 per 100,000 individuals (1, 2). Wider access and increased use of magnetic resonance imaging (MRI) and computed tomography (CT) has led to a marked rise in the number of incidental findings in clinical and research settings. Meningiomas comprise 15% of incidental findings on brain MRI and have a prevalence of 3/1000 (3). A recent study of the Surveillance, Epidemiology, and End Results (SEER) database demonstrated a substantial increase in the detection of smaller, incidental tumours; between 2004 and 2012, the proportion of <1 cm meningiomas diagnosed in a given year increased in a linear fashion from 6 to 11% (4). Incidental, asymptomatic meningiomas cause patient anxiety and uncertainty around the need for future treatment and often prompt clinicians to commence long-term MRI and clinical follow-up. International consensus guidelines by the European Association of Neuro-Oncology (EANO) and National Comprehensive Cancer Network (NCCN) suggest active monitoring with MRI as first line for managing these tumours (5, 6), but data to advise on the optimal follow-up duration and screening intervals is currently lacking (7).

Previous studies have identified prognostic radiological factors that are associated with the risk of meningioma growth and development of clinical symptoms; yet the timing of such progression is poorly defined (8-10). Moreover, clinical factors such as patient comorbidity and performance status remain unexplored in relation to prognosis but are highly relevant. The patient with an incidental meningioma wants to know whether their tumour will grow and become symptomatic such that it will require safe treatment within their healthy lifetime.

To this end, a recent retrospective cohort study of incidental meningioma patients in the United Kingdom (UK) was conducted to assess the utility of combining routinely available radiological and clinical factors to develop a prognostic model for the risk of incidental meningioma progression during active monitoring (11). The model IMPACT (Incidental Meningioma: Prognostic Analysis Using Patient Comorbidity and MRI Tests) could be used as a tool to guide active monitoring strategies for patients with an incidental asymptomatic meningioma within the first 10 years of diagnosis, however validation with external datasets is required.

This international retrospective cohort study of incidental meningioma has the primary aim of externally validating and calibrating the prognostic model IMPACT, accessible using <https://www.impact-meningioma.com>. These data will provide insight into the incidence, epidemiology, presentation, management, and long-term outcomes of incidental meningioma, which will inform the development of clinical guidelines and identify areas for future research.

1.1. THE IMPACT MODEL

The model, based on MRI parameters, stratifies patients with an incidental meningioma into three risk groups: low-, medium- and high-risk. These MRI parameters are as follows: meningioma volume, meningioma hyperintensity, peritumoral signal change and proximity to critical neurovascular structures. This predictive function was built using an internally validated cox regression model. Patients were also stratified in the model based on age, comorbidity and performance status using competing risk analyses.

2 OBJECTIVES

2.1. Primary objective

To externally validate the prognostic model IMPACT

2.2. Secondary objectives

- To update the parameters of the prognostic model IMPACT if measures of external validation demonstrate a poor fit
- To determine the growth patterns of incidental meningiomas
- To examine the MRI and pathology features of meningiomas subject to surgical resection
- To determine the risk of post-intervention complications and tumour recurrence/growth for meningiomas subject to surgery, stereotactic radiosurgery, or fractionated radiotherapy
- To assess the economic implications of stratifying follow-up according to risk of disease progression

3 METHODS

3.1. Study design

This will be a retrospective, international multicentre cohort study. The study will include incidental meningioma patients managed at each participating centre. Cases will be identified by the local site research teams using existing patient medical records. Baseline clinical and radiological characteristics, tumour management, and clinical and radiological outcomes will be collected and recorded (anonymised data) on a secure database by the local investigator. Since this study falls within the remit of clinical outcomes audit, individual patient consent is not required. The study will collect data from the medical records for patients newly-diagnosed over a 2-year period between 1st January 2009 and 31st December 2010. This is an observational study and will not impact on routine patient care.

3.2. Study population and eligibility criteria

The study will include adults (≥ 16 years of age) with a newly identified incidental intracranial meningioma, as per radiology report, diagnosed between 1st January 2009 and 31st

December 2010. Radiological diagnosis is expected to be based on the presence of an extra-axial lesion with broad-based attachment along the dura showing contrast enhancement. The accepted definition of an incidental finding is “a previously undetected abnormality of potential clinical relevance that is unexpectedly discovered and unrelated to the purpose of the examination”.

Exclusion criteria are as follows:

- History of cranial radiation >5 years from diagnosis
- History of neurofibromatosis type 2
- Surgical resection which revealed a different histopathological diagnosis
- Unavailability of medical notes including scans

3.3. Patient identification

Eligible patients can be identified using local radiology information systems, for example the Computerised Radiological Information System (CRIS) tool. The search strategy will involve review of the medical records of all patients managed with a meningioma at participating centres and exclusion of those that do not meet the selection criteria (Figure 1).

[figure not shown]

Figure 1. Process of creating a patient list at each study site

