3.10. Planned statistical analysis

3.10.1. External validation

Using IMPACT, the five- and ten-year estimated risk of disease progression for every patient included in this cohort study will be calculated. Kaplan-Meier method will be used to obtain the observed risks. The predictive performance of IMPACT will be assessed by examining measures of calibration and discrimination. Calibration refers to how closely the predicted 5- and 10-year risk of progression agrees with the observed risk. A calibration plot compares the observed and predicted rates of events for each group. A perfect match indicates accurate calibration. The Brier score for censored survival data will also be calculated, which is a measure of accuracy and is the average squared deviation between predicted and observed risk; a lower score represents greater accuracy. Discrimination is the ability of the risk score to differentiate between those patients who do and those who do not experience disease progression during the study timeframe. This measure is quantified by calculating the C-statistic, D-statistic and Chambless and Diao's time-dependent AUC (area under the receiver operating characteristic curve [ROC]) which are tailored towards censored survival data. Model assumptions will be tested by examination of Schoenfeld residuals, and influential observations will be examined using DFBETA panels.

The effect of patient age, comorbidity, and performance status on the risk of disease progression and intervention will be assessed using a competing risk analysis. Patients will be split based on WHO PS into two categories: 0-1 and 2-4 and stratified by ACCI (Table 1) into three groups: 0-2, 3-5 and ≥ 6 . An ACCI score of ≤ 2 corresponds to patients who are young (<60 years) with few or no comorbidities. An ACCI score of 3–5 corresponds to either an older patient with few comorbidities, or a younger patient with several comorbidities, and an ACCI score ≥ 6 denotes older patient with comorbidities (24).

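### Eligibility limits the date of diagnosis but not the place of diagnosis or date of first contact with the centre, so patients referred later because they progressed can enter and bias observed risk

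*Protocol*

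**What the plan says.** Protocol section 3.1 defines the cohort by where patients were managed: "The study will include incidental meningioma patients managed at each participating centre". It dates the diagnosis, taking "patients newly-diagnosed over a 2-year period between 1st January 2009 and 31st December 2010". Section 3.2 requires an adult "with a newly identified incidental intracranial meningioma, as per radiology report", without saying which hospital issued the report. Its four exclusions are earlier cranial radiation, neurofibromatosis type 2, a different histological diagnosis, and "Unavailability of medical notes including scans".

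Section 3.3 says "Eligible patients can be identified using local radiology information systems" and then describes the search: "The search strategy will involve review of the medical records of all patients managed with a meningioma at participating centres", followed by removal of those who do not meet the criteria, with a reference to Figure 1 (not shown).

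For the primary analysis, section 3.10.1 states that the "Kaplan-Meier method will be used to obtain the observed risks" at five and ten years, to be compared with the risks predicted by IMPACT. The cumulative incidence analyses in the same section are timed from diagnosis. Delayed entry is not mentioned.

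Appendix 1 restricts the year of the initial scan. It has no field for the place of diagnosis, the date of first contact with the participating centre, or the reason for referral.

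**The concern.** A validation cohort should be assembled without regard to what happened after time zero, which here is diagnosis in 2009-2010. The written criteria do not ensure this. Take two people with the same incidental meningioma, both found in 2010 at a hospital that is not a participating centre. One stays stable and is never referred. The other grows or becomes symptomatic and is referred to a participating centre in 2014. The second can be included, with time zero set back to 2010; the first cannot. Inclusion then depends on the outcome.

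The observed risk is the yardstick for the primary objective. If it is too high, a well-calibrated model appears to under-predict. Section 3.10.2 makes poor fit the trigger for recalibration and stepwise removal of predictors, so a selection effect could lead to changes in the model itself. The cumulative incidence of intervention is exposed in the same way, since progression can prompt both referral and treatment.

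The problem could not be repaired reliably at analysis. Appendix 1 records scan dates, so a long gap after the first scan might suggest a late referral, but it would not separate one from a long monitoring interval at the same centre.

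**Working it through.** **Step 1. Does any written rule close the gap?**

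| Place in the protocol | What it restricts | Does it remove a patient referred after progression? |
|---|---|---|
| 3.1 | Date of diagnosis | No |
| 3.2, inclusion | Age, incidental finding, radiology report | No; source of the report not stated |
| 3.2, exclusions | Radiation, NF2, histology, unavailable notes or scans | Only if the index notes or scans cannot be obtained |
| 3.3 | Local radiology search offered as an option; all managed meningioma patients reviewed | Not as a rule |
| Appendix 1 | Year of initial scan | No |

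**Step 2. The plan's own figure.** Section 3.4 needs 100 events at a 10% risk: 100 / 0.10 = 1000 patients, which agrees with the text. At the stated minimum of 1500, expected events are 1500 x 0.10 = 150.

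**Step 3. Crude effect.** Inputs: the 10% risk from section 3.4; f, the share of the cohort that are late referrals (assumed); q, the share of those who progressed (assumed).

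Observed crude risk = 0.10(1 - f) + qf

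| | f = 1% (15 of 1500) | f = 5% (75 of 1500) |
|---|---|---|
| q = 1 | 0.099 + 0.010 = 10.9% | 0.095 + 0.050 = 14.5% |
| q = 0.5 | 0.099 + 0.005 = 10.4% | 0.095 + 0.025 = 12.0% |
| q = 0.1 | 0.099 + 0.001 = 10.0% | 0.095 + 0.005 = 10.0% |
| q = 0 | 9.9% | 9.5% |

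The shift equals f(q - 0.10), so its sign depends on whether late referrals progressed more or less often than 10%.

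**Step 4. Effect on the planned estimator.** The formula is a crude proportion, whereas the plan uses Kaplan-Meier. A simulation of 1500 patients (60 repetitions) assumed a constant hazard giving 10% risk at 10 years, ordinary patients censored uniformly between 2 and 11 years, and every late referral an event, uniform over 2 to 10 years, with no delayed entry.

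| f | 5-year, without / with late referrals | 10-year, without / with |
|---|---|---|
| 1% | 5.2% / 5.6% | 10.0% / 12.5% |
| 5% | 5.2% / 7.1% | 10.0% / 21.1% |

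The 10-year estimate moves more because late events fall where few patients remain at risk. This illustrates the q = 1 case only; referral times and censoring are assumptions.

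**The case against.** The strongest reply is that the selection process is delegated to Figure 1, which is captioned as the process for building the patient list and is not shown. It may contain the missing filter. The synopsis speaks of patients at participating centres diagnosed in the window, which can be read as patients already under the centre at diagnosis, and the suggested tool is the local radiology system. This stands as a condition on the point, but sections 3.1 to 3.3 should still state any such rule. The synopsis wording is compatible with both readings, and the radiology search is optional.

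Second, not every late referral would qualify. The exclusion for unavailable notes or scans, together with the baseline measurements required by Appendix 1, removes those whose index records cannot be retrieved. This stands and reduces f, but it does not remove the others.

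Third, a reader might infer that observed risk is inflated by 9% to 45%, the relative excess at q = 1 for f of 1% to 5%. The documents do not support that as an estimate: they give neither f nor q. Stable patients who arrive late, for example after moving house, add event-free time and pull the estimate down.

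Fourth, delayed entry is commonly left to a statistical analysis plan. That is fair for the method, but eligibility and collected fields are set in the protocol, and later analysis cannot recover a date that was never collected.

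**Conclusion.** The point holds, conditional on Figure 1. Sections 3.1 to 3.3 admit any patient managed at a participating centre with a 2009-2010 diagnosis and obtainable index records, whenever and for whatever reason the patient arrived. This permits outcome-dependent entry into the primary calibration and the intervention analysis, and Appendix 1 does not collect what is needed to detect it.

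The direction is upward when progression drives the referral; it is not established for late arrivals in general. The size cannot be derived from the documents, and the tables above show a range under assumed f and q. Nor should a reader infer that left truncation would settle the matter. When progression prompts the referral, the event precedes or nearly coincides with first contact. Such a patient either has no time at risk after entry or enters and fails almost at once.

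**What to change.** In sections 3.2 and 3.3, consistent with Figure 1, require that the diagnostic scan was done at the participating centre, or that first referral there fell within a short prespecified interval of that scan and before any progression or intervention. Add the date and reason of first contact with the centre to Appendix 1.

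If later entrants are kept, include only those free of progression and intervention at first contact, let them enter the risk set from that date, and report a sensitivity analysis without them.

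The cost is one eligibility sentence and two short data fields. A few late-referred patients would be lost or would contribute less follow-up.

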3.4. Sample size

For external validation studies, a minimum of 100 events is required (12). The risk of incidental meningioma progression is estimated to be 10% (11). Based on this, data for 1000 patients will be required. To account for variability in the progression risk, follow-up regimes and loss to follow-up, we will include a minimum of 1500 patients across participating centres.

3.5. Study endpoints

3.5.1. Primary endpoint

Disease progression will be defined using a composite endpoint comprising of new symptom development, meningioma-specific mortality, meningioma growth (absolute growth rate ≥ 2 cm³/year or absolute growth rate ≥ 1 cm³/year + relative growth rate $\geq 30\%$ /year), development or increase of peritumoural brain oedema (defined as increased signal intensity on T2/FLAIR), venous sinus invasion and meningioma volume exceeding 10 cm³. The first two criteria denote clinical progression while the latter three are related to loss of window of curability. Venous sinus invasion and peritumoural oedema can prevent complete surgical resection (13, 14). Peritumoural oedema and a meningioma volume >10 cm³ are relative contraindications to stereotactic radiosurgery (15, 16).

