3.8.2. Baseline radiological variables

Baseline imaging variables assessed will be:

- Single or multiple intracranial meningioma
- Tumour signal intensity compared to the contralateral grey matter on fluid attenuated inversion recovery (FLAIR) and T2-weighted (T2) MRI (hypo/iso/hyper) (Figure 2)
- Peritumoural signal intensity in relation to tumour volume using the signal change present on FLAIR and T2 MRI (0-5%/6-33%/34-66%/67-100%; adapted from the VASARI [Visually AcceSAbLe Rembrandt Images] MR features for gliomas (20))
- Meningioma volume using the ABC/2 formula on contrast-enhanced T1-weighted MRI/CT: (A) maximum meningioma diameter on axial plane, (B) diameter perpendicular to (A) and (C) maximum height on coronal/sagittal plane, not taking into the account the dural tail
- Meningioma location classed into non-skull base and skull base and further subcategorised according to the ICOM (International Consortium on Meningioma) classification system (Appendix 2)
- Proximity to major dural venous sinuses (superior sagittal sinus/transverse sinus/sigmoid sinus/cavernous sinus/the confluence of sinuses) categorised as separate (within 10 mm), in direct contact with its wall, or invading, excluding the dural tail (Figure 2)
- Contact with critical neurovascular structures (i.e. internal carotid artery and optic apparatus)

Meningiomas that fulfil one of the two previous categories are said to be in proximity to critical neurovascular structures. A video manual prepared by the study team will be made available to assist with standardisation and quality assurance of scan interpretation across participating centres.

[figure not shown]

Figure 2. (A-C) T2 MR axial sequences showing the 3 levels of tumour intensity (circle). (A) Hypointense. (B) Isointense. (C) Hyperintense. (D-F) T1-weighted MR with gadolinium (contrast) showing the relationship between the meningioma and the nearby venous sinus (SSS). (D) Separate as there's no clear attachment to the sinus wall. (E) In direct contact with the lateral wall of the sinus. (F) Clear macroscopic distortion and invasion of the sinus.

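### The primary endpoint does not require venous sinus invasion or volume above 10 cm³ to be new since the baseline scan, and no rule covers patients who have either at diagnosis

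*Protocol*

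**What the plan says.** Protocol section 3.5.1 defines disease progression as a composite of six components. Two are explicitly worded as changes: "new symptom development" and "development or increase of peritumoural brain oedema". Growth is given as a rate, so it too is a change. The last two carry no reference to the baseline scan: "venous sinus invasion and meningioma volume exceeding 10" cm³. The section then explains that "the latter three are related to loss of window of curability", meaning oedema, sinus invasion and volume.

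Other sections bear on how this is scored:

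- Section 3.2 has four exclusions (earlier cranial radiation, neurofibromatosis type 2, a different histological diagnosis, unavailable notes or scans). None concerns baseline volume or sinus invasion.
- Section 3.8.2 records volume at baseline with no upper limit, and sinus relation "categorised as separate (within 10 mm), in direct contact with its wall, or invading, excluding the dural tail". Invasion is therefore a permitted baseline grade.
- Section 3.8.3 and Appendix 1 record both again on each monitoring scan. The monitoring form asks whether symptoms are new; for sinus relation and diameters it captures only the current state.
- Section 1.1 gives the model's predictors as "meningioma volume, meningioma hyperintensity, peritumoral signal change and proximity to critical neurovascular structures".
- Section 1 says the model concerns "the risk of incidental meningioma progression during active monitoring".
- Section 3.10.1 calculates a predicted risk for every included patient and gives no rule for those who already meet a component at diagnosis.

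**The concern.** Where the authors wanted a change they wrote one, so within the same sentence the natural reading of the last two components is that presence is enough. A tumour already above 10 cm³, or already graded as invading, would then meet the primary endpoint at its first follow-up scan without having changed. That does not fit an endpoint justified by loss of curability, or a model meant for progression under monitoring.

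The primary objective is at stake. Findings present at diagnosis would enter the observed 5- and 10-year risks, against which calibration is judged. For volume there is a second problem: in a tumour already above 10 cm³, the predictor and the outcome are the same measurement, so the model is credited with predicting something it was told. Section 3.10.2 makes recalibration depend on these performance measures, so a misjudged fit could wrongly trigger or prevent it.

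**Working it through.** **1. The plan's own figure.** Section 3.4 asks for 100 events at a progression risk of 10%: 100 / 0.10 = 1000 patients, as stated. The planned minimum of 1500 gives 1500 × 0.10 = 150 events.

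**2. How easily the volume threshold is met.** Section 3.8.2 uses ABC/2. With three equal diameters d, d³/2 = 10 gives d = cube root of 20, about 2.7 cm.

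**3. Literal scoring.** Let q be the share of patients positive at baseline on either finding. The protocol gives no value, so q is assumed. Take 10% as the risk of a new event in the others, and count every baseline-positive patient as an event.

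- Prevalent events = 1500q
- Incident events = 1500(1 − q) × 0.10 = 150(1 − q)
- Apparent risk = q + 0.10(1 − q)

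| q | Prevalent | Incident | Prevalent share of events | Apparent risk |
|---|---|---|---|---|
| 2% | 30 | 147 | 30/177 = 17% | 11.8% |
| 5% | 75 | 142.5 | 75/217.5 = 34% | 14.5% |
| 10% | 150 | 135 | 150/285 = 53% | 19% |

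The prevalent events fall at the baseline or first follow-up scan, so they generally raise both the 5-year and the 10-year observed risk.

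**4. Effect on discrimination.** This was checked on simulated cohorts of 1500 (30 replicates per scenario, Harrell's C). Assumptions: log-normal volume, proximity in 40%, hyperintensity in 30%, one common coefficient b for all three predictors, events from the other components in about 10% by 10 years, and censoring spread over 1 to 11 years. Baseline-positive patients were either counted as immediate events (literal) or excluded. Each cell shows C, literal v excluded.

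| Positive at baseline | b = 0 | b = 0.3 | b = 0.6 | b = 0.9 |
|---|---|---|---|---|
| Volume 5%, almost no invasion | 0.76 v 0.50 | 0.81 v 0.61 | 0.86 v 0.70 | 0.89 v 0.79 |
| Volume 5%, invasion 3% | 0.74 v 0.51 | 0.77 v 0.62 | 0.80 v 0.70 | 0.83 v 0.79 |
| Invasion 5%, almost no volume above 10 cm³ | 0.58 v 0.50 | 0.62 v 0.61 | 0.67 v 0.73 | 0.72 v 0.82 |

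C rises in every scenario with an appreciable share above 10 cm³, even when the model has no true predictive value (b = 0). Invasion alone raises C when the model is weak and lowers it when the model is strong. The reason is that the proximity predictor is coarse: section 3.8.2 pools tumours near, touching or invading a sinus with those touching the carotid artery or optic apparatus. Only C was simulated. The D-statistic and time-dependent AUC rank the same patients against the same outcome, so volume pushes them the same way.

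**5. Event count after the fix.** If all baseline-positive patients are excluded, incident events are 150(1 − q). This is at least 100 while q ≤ 1 − 100/150 = 1/3.

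**The case against.** The strongest reply is that no section states that baseline-positive patients are events. The endpoint is called progression, its rationale speaks of a loss, and the model is described for use during monitoring; all three suggest that new findings were meant. The word for development in the oedema component might be carried over to invasion, and exceeding 10 cm³ might be read as crossing it. Both findings are recorded at baseline and at follow-up, so change can be derived, and a separate analysis plan might settle the matter.

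Much of this stands. A reader might infer that the protocol lays down a rule counting such patients as progressed. It does not; that follows only from the literal wording. But the probable intent is a reason to correct the text, not a substitute for doing so. What counts as a primary event is fixed in section 3.5.1, and data from many centres will be scored against it.

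Three further points also stand. Section 3.8.3 and Appendix 1 allow immediate intervention or discharge, so some baseline-positive patients may never have a monitoring scan, and the shares above may be too high. An external validation should use the endpoint on which the model was developed, and this document does not show how that study scored findings present at diagnosis. Finally, assessing baseline-positive patients on the other components alone leaves the largest tumours fewer ways to have an event, which could lower observed risk where predicted risk is high.

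**Conclusion.** The point holds as a defect in the primary endpoint's wording. Two components are not required to be new, nobody is excluded for having them at diagnosis, and no handling rule is given. Followed literally, the text raises observed risk and distorts calibration, and through volume it inflates discrimination.

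The size cannot be derived from the protocol. The shares and apparent risks in the working assume the baseline prevalence, a 10% risk of new events, and that every baseline-positive patient is scored as an event. The simulated C values also rest on an assumed volume distribution and assumed coefficients.

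Two stronger readings are tempting and are not supported. One is that baseline invasion also inflates discrimination: alone, it moved C in either direction. The other is that the 100-event target fails once prevalent findings are removed: at a 10% risk of new events it is still met unless more than about one third of patients are positive at baseline.

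**What to change.** Reword the two components in section 3.5.1 along these lines: *new venous sinus invasion (not graded invading on the baseline scan) and meningioma volume newly exceeding 10 cm³ (baseline volume ≤10 cm³)*.

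State that patients with either finding at baseline stay in the cohort and are assessed on the remaining components. Add a sensitivity analysis that excludes them, because they have fewer ways to have an event.

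Confirm whether this rule matches the development study's endpoint. If it does not, report calibration and discrimination under both definitions side by side, so that the like-for-like comparison with the model's predicted risks is kept.

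The cost is a short rewording, a statement of the handling rule and one extra analysis, plus a second set of performance measures if the definitions differ. The fields needed are already collected. There will be somewhat fewer events than under literal scoring.
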